[54] have evidence of latent TB (as documented by a positive PPD, no clinical symptoms consistent with active TB, and a normal chest x-ray at screening) unless patients complete at least 4 weeks of appropriate treatment prior to randomization and agree to complete the remainder of treatment while in the trial

- a. If the PPD test is positive and the patient has no medical history or chest x-ray findings consistent with active TB, the patient may have a QuantiFERON-TB Gold or T-SPOT.TB_test (if available). If the test results are not negative, the patient will be considered to have latent TB (for purposes of this study).
- b. The QuantiFERON-TB Gold or T-SPOT.TB_test (if available) may be used instead of the PPD test. If the test results are positive, the patient will be considered to have latent TB. If the test is not negative, the test may be repeated once within approximately 2 weeks of the initial value. If the repeat test results are again not negative, the patient will be considered to have latent TB (for purposes of this study).
- c. Exceptions include patients with a history of active or latent TB who have documented evidence of appropriate treatment.

[55] have a positive test for HBV defined as:

- a. positive for hepatitis B surface antigen, **or**
- b. positive for anti-hepatitis B core antibody but negative for hepatitis B surface antibody (HBsAb), **or**
- c. for patients enrolled in other countries, if required, positive for anti-HBsAb and positive for HBV deoxyribonucleic acid (DNA).

If any of the HBV tests have an indeterminate result, confirmatory testing will be performed by an alternate method.

[56] have HCV (positive for anti-hepatitis C antibody with confirmed presence of HCV)

[57] have evidence of human HIV infection and/or positive HIV antibodies

[58] Are women ≥ 40 and < 60 years of age who have had a cessation of menses for at least 12 months, have a follicle-stimulating hormone (FSH) value < 40 mIU/mL, and do not agree to use 2 forms of highly effective methods of birth control when engaging in intercourse while enrolled in the study and for at least 28 days following the last dose of orally administered investigational product, unless they are congenitally or surgically sterile (that is, have had a hysterectomy, bilateral oophorectomy, or tubal ligation)

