8.3.1.2. Discontinuation of Study Drug

Any patient who is permanently discontinued from study drug for an AE or abnormal laboratory result should have the AE or abnormal laboratory value reported as an SAE (reported as Other Reason Serious). If any of the criteria listed in Section 8.3.1.1 above recur after study drug is restarted, the patient should be permanently discontinued from study drug. In addition, patients will be permanently discontinued from study drug if they experience any of the criteria listed in [Table JAGS.8.2](#).

Table JAGS.8.2. Criteria for Permanent Discontinuation of Investigational Product

Permanently Discontinue Investigational Product if any of the Following are Observed:
ALT or AST >8 times the ULN
ALT or AST >5 times the ULN persisting for more than 2 weeks after temporary interruption of investigational product
ALT or AST >3 times the ULN and total bilirubin level >2 times the ULN
ALT or AST >3 times the ULN with the appearance of fatigue, nausea, vomiting, right upper quadrant pain or tenderness, fever, rash, and/or eosinophilia (>5%)
WBC count <1000 cells/ μ L
Absolute neutrophil count <500 cells/ μ L
Lymphocyte count <200cells/ μ L
Hemoglobin <6.5 g/dL
Symptomatic herpes zoster
Pregnancy
Malignancy
HBV DNA \geq 29 IU/mL ^a
Severe infection that, in the opinion of the investigator, merits the investigational product being discontinued

Abbreviations: ALT = alanine aminotransferase; AST = aspartate aminotransferase; ULN = upper limit of normal; WBC = white blood cell.

^a. If an HBV DNA result of “target detected” 29 IU/mL or greater, then the patient should be referred to a hepatology specialist immediately. In selected cases, investigators may temporarily continue study drug in accordance with current immunomodulator management in the setting of HBV DNA positivity. This option may be considered in consultation with Lilly (or its designee) and evaluation of individual patient risks and benefits. Refer to Section 10.3.2.2 for additional instruction on HBV DNA monitoring.

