10.3.2.2. Measures Evaluated During Screening and Treatment Periods

Vital signs and physical characteristics. Vital signs (sitting blood pressure and heart rate) will be measured at times indicated in the Study Schedule ([Attachment 1](#)). Subjects should be seated and relaxed with both feet on the floor for at least 5 minutes prior to taking measurements. Three replicate blood pressure readings should be made at each time point at approximately 30- to 60-second intervals. A single pulse measurement should be taken simultaneously with at least one of the blood pressure readings. Blood pressure and pulse measurements should be made using either automated or manual equipment. If measurements are machine averaged, the average blood pressure reading should be recorded on the CRF. If measurements are manual or the machine does not provide an average reading, then each individual reading should be recorded on the CRF. Measurements should be made before any scheduled blood draws. Any clinically significant findings that result in a diagnosis should be captured on the CRF and reported as an AE. Additional measurements of vital signs may be performed at the discretion of the investigator. Physical characteristics including weight and waist circumference will be measured at times indicated in the Study Schedule ([Attachment 1](#)).

Standard laboratory tests. Hematology, clinical chemistry, urinalysis, lipid profile, eGFR, iron studies, hsCRP, and ESR will be measured at times indicated in the Study Schedule ([Attachment 1](#)).

Hepatitis B virus (HBV) DNA monitoring: Patients who were hepatitis B core antibody (HBcAb) positive at screening will require HBV DNA monitoring as indicated in the study schedule ([Attachment 1](#)). If an HBV DNA result of “target detected” ≥ 29 IU/mL, then the patient should be referred to a hepatology specialist immediately. In selected cases, investigators may temporarily continue study drug in accordance with current immunomodulator management in the setting of HBV DNA positivity. This option may be considered in consultation with Lilly (or its designee) and evaluation of individual patient risks and benefits.

The following actions should be taken in response to HBV DNA test results:

- If a result of “target detected” is obtained at any time during the study with a value of ≥ 29 IU/mL, refer to [Table JAGS.8.2](#)

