- If a single result of “target detected” is obtained with a value of < 29 IU/mL, the test should be repeated within approximately 2 weeks.
 - If the repeat test result is “target not detected,” monitoring may resume according to the study schedule.
- If the patient has two or more test results of “target detected” with a value of < 29 IU/mL at any time, HBV testing should be conducted approximately once per month for the remainder of the study and referral to a hepatologist is recommended.

The additions to the Study Schedule and table of Clinical Laboratory Tests are shown in [Attachment 1](#) and [Attachment 2](#).

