	Screening		Blinded, Placebo- Controlled Treatment Part A										Open-label Part B					Follow-up Part Ca
Visit	1	1a	2	3	4	5	6	7	8	9	10	11	12	13	14	15	ET	801
Week of Treatment			Base- line 0	1	2	4	8	12	14	16	20	24	28	32	40	52	Any week	
Days from Visit 2	-42 to -3 days		0	7 ± 2 days	14 ± 2 days	28 ± 2 days	56 ± 3 days	84 ± 3 days	98 ± 3 days	112 ± 3 days	140 ± 3 days	168 ± 3 days	196 ± 3 days	224 ± 5 days	280 ± 5 days	365 ± 5 days	Any day	28 ± 5 days after last dose
Physician global assessment of disease activity			X	X	X	X	X	X	X	X	X	X	X	X	X	X	X	X
Hand and foot x-rays ⁱ	X ⁱ									X		X				X	X ⁱ	
HAQ-DI			X	X	X	X	X	X	X	X	X	X	X	X	X	X	X	X
Morning joint stiffness - diary			X ^k															
Morning joint stiffness - tablet ^l			X	X	X	X	X	X	X	X	X	X	X	X	X	X	X	X
FACIT-F			X			X	X	X		X	X	X	X	X	X	X	X	X
EQ-5D-5L			X			X	X	X		X	X	X	X	X	X	X	X	X
Worst tiredness NRS-diary			X ^k															
Worst tiredness NRS-tablet ^l			X	X	X	X	X	X	X	X	X	X	X	X	X	X	X	X
WPAI-RA			X		X	X	X	X		X	X	X	X	X	X	X	X	X
Worst joint pain NRS-diary			X ^k															
Worst joint pain NRS-tablet ^l			X	X	X	X	X	X	X	X	X	X	X	X	X	X	X	X
QIDS-SR16			X					X				X				X	X	X
Healthcare resource use			X			X	X	X		X	X	X	X	X	X	X	X	X
Laboratory tests																		
TSH	X																	
HIV	X																	
Hepatitis C antibody testing	X																	
Hepatitis B testing (HBsAg, HBcAb, HBsAb)	X																	

Visit	Screening		Blinded, Placebo- Controlled Treatment Part A										Open-label Part B				ET	Follow-up Part Ca
	1	1a	2	3	4	5	6	7	8	9	10	11	12	13	14	15		
Week of Treatment			Base-line 0	1	2	4	8	12	14	16	20	24	28	32	40	52	Any week	
Days from Visit 2	-42 to -3 days		0	7 ± 2 days	14 ± 2 days	28 ± 2 days	56 ± 3 days	84 ± 3 days	98 ± 3 days	112 ± 3 days	140 ± 3 days	168 ± 3 days	196 ± 3 days	224 ± 5 days	280 ± 5 days	365 ± 5 days	Any day	28 ± 5 days after last dose
Serum pregnancy test ^m	X		X															
Urine pregnancy test ^m			X	X	X	X	X	X	X	X	X	X	X	X	X	X	X	X
FSH ⁿ	X																	
Clinical chemistry ^o	X		X	X	X	X	X	X	X	X	X	X	X	X	X	X	X	X
Lipid panel ^p			X					X				X				X		
Lipid NMR ^q			X					X										
Hematology	X		X	X	X	X	X	X	X	X	X	X	X	X	X	X	X	X
HBV DNA ^r								X				X		X	X	X	X ^s	
Iron studies (iron, TIBC, and ferritin)	X		X					X				X				X		
Urinalysis	X		X					X				X		X		X	X	
Rheumatoid factor	X		X					X				X				X	X	
hsCRP	X		X	X	X	X	X	X	X	X	X	X	X	X	X	X	X	X
Erythrocyte sedimentation rate ^t	X		X	X	X	X	X	X	X	X	X	X	X	X	X	X	X	X
Anti-CCP	X		X					X				X				X	X	

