- m For all women of childbearing potential, a serum pregnancy test (central laboratory) will be performed at Visit 1 and Visit 2. Urine pregnancy tests (local laboratory) will also be performed at Visit 2 and at all subsequent study visits.
- n To confirm postmenopausal status for women ≥ 40 and < 60 years of age who have had a cessation of menses, an FSH test will be performed. Nonchildbearing potential will be defined as an FSH ≥ 40 mIU/mL and a cessation of menses for at least 12 months.
- o Clinical chemistry will include the following values calculated from serum creatinine: calculated creatinine clearance (Cockcroft-Gault equation) and eGFR (calculated using the Modification of Diet in Renal Disease isotope dilution mass spectrometry traceable method).
- p Fasting lipid profile. Patients should not eat or drink anything except water for 12 hours prior to sample collection. If a patient attends these visits in a nonfasting state, this will not be considered a protocol violation.
- q Lipid NMR tests will not be performed at sites in China. Other participated countries will have this tests.
- r HBV DNA monitoring will be performed in patients who tested positive for HBcAb at screening.
- s To be performed only if previous test was more than 3 months earlier.
- t Erythrocyte sedimentation rate will be performed locally using a kit provided by the sponsor.

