- a Assayed/calculated by a sponsor-designated laboratory.
- b Unscheduled blood chemistry (including CPK), hematology, and urinalysis panels may be performed at the discretion of the investigator. If tests are done to evaluate laboratory results to resume study drug, samples must be assayed centrally.
- c Estimated glomerular filtration rate for serum creatinine calculated by the central laboratory using the Modification of Diet in Renal Disease isotope dilution mass spectrometry traceable method.
- d The calculated creatinine clearance will be determined by the central laboratory each time a serum creatinine sample is collected using the Cockcroft-Gault equation: Men: $([140 - \text{age}] \times [\text{weight in kg}]) / (72 \times [\text{serum creatinine in mg/dL}])$ or $([140 - \text{age}] \times [\text{weight in kg}]) / (0.814 \times [\text{serum creatinine in } \mu\text{mol/L}])$. Women: $(\text{above formula}) \times 0.85$.
- e Fasting laboratory values for glucose and lipids will be required at baseline, Week 12, Week 24, and Week 52. If a patient attends these visits in a nonfasting state, this will not be considered a protocol violation. These tests may be performed nonfasting at all other visits.
- f For all women of childbearing potential, a serum pregnancy test (central laboratory) will be performed at Visit 1 and both urine (local laboratory) and serum pregnancy (central laboratory) tests will be performed at Visit 2 to determine study eligibility. Urine pregnancy tests (local laboratory) will also be performed at each subsequent study visit per study schedule.
- g To confirm postmenopausal status for women ≥ 40 and < 60 years of age, an FSH test will be performed. Nonchildbearing potential is defined as an FSH ≥ 40 mIU/mL and a cessation of menses for at least 12 months.
- h A positive hepatitis C antibody result will be confirmed with a positive hepatitis C virus result.
- i Microscopic examination of sediment will be performed only if abnormalities are noted on the routine urinalysis.
- j Test will be required at Visit 1 only to determine eligibility of patient for the study. In countries where the QuantiFERON-TB Gold or T-SPOT.TB test is available and, in the judgment of the investigator, medically preferred as an alternative to the PPD test for the evaluation of mycobacterium tuberculosis (MTB) infection, it may be used instead of the PPD test (positive tests excluded) and may be read locally.

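### HBcAb-positive patients can be randomised with no scheduled HBV DNA test before dosing; outside undefined local requirements, the first fixed-visit test is at Week 12

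*Protocol*

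**What the plan says.** **Eligibility.** Criterion [55] in Protocol Section 8.2.2 has three limbs. Limb (a) excludes anyone HBsAg-positive. Limb (b) excludes a patient who is "positive for anti-hepatitis B core antibody but negative for hepatitis B surface antibody (HBsAb". Limb (c) excludes on HBV DNA, but only "for patients enrolled in other countries, if required, positive for anti-HBsAb and positive for HBV deoxyribonucleic acid (DNA". The protocol does not say which countries are meant or what makes the test required.

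**Schedule.** The Visit 1 row in Attachment 1 is "Hepatitis B testing (HBsAg, HBcAb, HBsAb", which is serology only. HBV DNA has its own row, first marked at Visit 7. Footnote r says who is tested: "HBV DNA monitoring will be performed in patients who tested positive for HBcAb at screening". Section 10.3.2.2 leaves the timing to the schedule. Attachment 2 lists the HBV DNA assay without naming a visit.

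**Action rules.** Table JAGS.8.2 lists HBV DNA of 29 IU/mL or more among the criteria for permanent discontinuation. Its footnote a calls for immediate hepatology referral and, in selected cases, lets drug continue temporarily. Section 10.3.2.2 applies the threshold to a detected result that "is obtained at any time during the study with a value of" 29 IU/mL or more. For a single detected value below 29, "the test should be repeated within approximately 2 weeks".

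**The concern.** The protocol itself treats HBcAb-positive patients as a group that needs virological monitoring, and it sets a numerical stopping threshold for them. Yet nothing it schedules can show, before the first dose, whether a patient already exceeds that threshold. Two things are at stake.

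- **Patient safety.** A patient with undetected viraemia could take a JAK inhibitor for about 12 weeks before the rule written for that situation has a result to act on.
- **Interpretation of safety data.** SAP Section 6.14.1 judges treatment-emergence against the period before first dose, and SAP Section 6.14.4.6 names viral hepatitis as a treatment-emergent infection category. With no pre-dose HBV DNA value, viraemia first found at Week 12 could be old or could be on-treatment reactivation. If it is reported as a new event, it counts as treatment-emergent by default.

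**Working it through.** The plan gives no figure for this point, so the check is of eligibility logic and schedule columns.

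**1. Who gets through [55].**

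| HBsAg | HBcAb | HBsAb | Outcome |
|---|---|---|---|
| + | any | any | excluded by (a) |
| − | + | − | excluded by (b) |
| − | + | + | passes (a) and (b); HBV DNA matters only where (c) is in force |

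Every correctly randomised HBcAb-positive patient is therefore HBsAg-negative and HBsAb-positive. This is the group that footnote r sends for HBV DNA monitoring.

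**2. Where the first HBV DNA mark falls.** Counting visit columns from the left, columns 1, 2 and 3 are Visits 1, 1a and 2. The HBV DNA row has its first mark in column 8. The lipid panel row gives an alignment check: it is marked in columns 3, 8, 12 and 16, and Attachment 2 footnote e states in words that "Fasting laboratory values for glucose and lipids will be required at baseline, Week 12, Week 24, and Week 52". So column 3 is baseline and column 8 is Week 12. The schedule reprinted in Attachment 4 agrees on this part of the row. Pre-dose cells: 3 columns × 2 printings = 6, of which 0 are marked. The printings differ only on later marks, and nothing here depends on those.

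**3. Time to the first fixed-visit test.** Visit 7 is Day 84 ± 3.
- From first dose: 84 − 3 = 81 days to 84 + 3 = 87 days; 81/7 = 11.6 and 87/7 = 12.4 weeks.
- From Visit 1 serology: screening lasts at least 3 days, so at least 81 + 3 = 84 days. There is no fixed maximum, because Section 7.1.1 lets the 42-day window be extended in exceptional circumstances.

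**4. What the patient takes meanwhile.** Allocation is 1:1 (Section 9.3), so an affected patient has a 50% chance of being on baricitinib.

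**5. What is measured earlier.** Clinical chemistry is drawn at Visits 3, 4, 5 and 6 (Weeks 1, 2, 4 and 8), which is four draws. None includes HBV DNA.

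**6. How many patients.** The expected number is 288 × p × q, where p is the share of randomised patients who are HBcAb-positive and HBsAb-positive, and q is the viraemic share among them. The documents give neither, so no count is claimed.

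**The case against.** Four points can be made against the concern.

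*Liver safeguards operate before Week 12.* Table JAGS.8.1 holds drug at ALT or AST above 5 times ULN. Table JAGS.8.2 stops it above 8 times ULN, or above 3 times ULN with bilirubin above 2 times ULN or with symptoms. Section 10.3.3 starts hepatic monitoring at 3 times ULN, and Attachment 3 then offers repeat hepatitis B serology. Entry criteria [22], [25], [31], [32], [49], [50] and [60] also remove some patients with liver disease, hepatitis B history, abnormal laboratory values or active infection. This stands, and it limits the exposure. But these rules respond to liver injury, history or clinical judgement. The protocol already draws chemistry at every visit and still requires HBV DNA testing in this group, so it does not treat chemistry as a substitute.

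*Limb (c) presupposes a pre-randomisation result somewhere.* This also stands. Where a site applies (c), a DNA-positive patient is excluded. The number of such sites cannot be established, and Attachment 1 does not schedule the test that they would need.

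*Harm is not quantified.* This is correct. The intervals above describe the schedule, not the risk, and the group is narrow because limbs (a) and (b) already remove the other serological patterns.

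*A Visit 1 test alone would not be enough.* This is also correct. A reader might infer that Table JAGS.8.2 and its footnote a would deal with a positive screening result. They govern patients already on drug. Of continuing drug temporarily, footnote a says "This option may be considered in consultation with Lilly (or its designee) and evaluation of individual patient risks and benefits"; it says nothing about eligibility. Outside (c), a viraemic screenee would meet no HBV DNA exclusion and could be kept out only by a discretionary criterion such as [49].

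**Conclusion.** The concern holds as a gap between the eligibility criteria and the schedule. HBsAg-negative, HBcAb-positive, HBsAb-positive patients are admitted with no HBV DNA test scheduled before dosing, and limb (c) depends on a result that Attachment 1 never asks for. Except where (c) is applied locally, a patient at or above 29 IU/mL can take 11.6 to 12.4 weeks of blinded drug before the first fixed-visit test. A patient who leaves earlier might be tested at early termination, but that is also after dosing.

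Three stronger readings are tempting, and the documents do not support them:
- *No pre-dose HBV DNA test is done anywhere.* Limb (c) implies that some sites test.
- *Patients are unprotected until Week 12.* Only the HBV DNA rule lacks data until then; the liver-enzyme rules act from Week 1.
- *The trial's results are biased.* Assignment is randomised and blinded, and power and the efficacy analyses do not use HBV DNA. The interpretive loss is confined to classifying hepatitis B findings.

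The conclusion rests on the printed schedule and on there being no unpublished country-specific instruction that requires the test. It is worth correcting for patient safety, and it does not call the main comparison into question.

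**What to change.** 1. In Attachment 1 and footnote r, add a reflex HBV DNA test on Visit 1 blood for HBcAb-positive screenees, and for HBsAb-positive screenees where [55](c) is locally required. The result should be reviewed before randomisation.
2. Extend [55](c) to HBcAb-positive, HBsAb-positive patients in all countries, and define a positive result. A value of 29 IU/mL or more excludes the patient and leads to hepatology referral. A detected value below 29 IU/mL may be repeated once within about 2 weeks, with randomisation only if the repeat detects no target. Limb (c) now has no threshold, and the repeat rule in Section 10.3.2.2 has no eligibility outcome, so both need this wording to agree.
3. Do not rely on Table JAGS.8.2 footnote a for patients who have not been dosed.

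The cost is one extra run of an assay already listed in Attachment 2, in a subset of screenees, with no new visit or procedure. There would be a short wait within screening and a few more screen failures. No sample size or analysis changes.

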8.2.3. Rationale for Exclusion of Certain Study Candidates

The rationale for the **entry** Exclusion Criteria is as follows: Exclusion Criteria [7] to [16] exclude individuals who are taking or who may take RA medications or treatments that interfere with the ability to assess the safety and efficacy of baricitinib. Exclusion Criteria [17] to [26] exclude individuals with previous or concomitant medical conditions that increase the risk for their participation in the study. Exclusion Criteria [27] to [34] exclude individuals who are at an increased risk for infections or infectious complications. Exclusion Criteria [35] to [37] exclude individuals who are pregnant, breastfeeding, at risk for becoming pregnant, or at risk for impregnating their partner during the study. Exclusion Criteria [38] to [45] exclude individuals who may not be compliant with study-related procedures or whose participation in the study may introduce bias.

The rationale for the **enrollment** Exclusion Criteria is as follows: Exclusion Criteria [49] to [52] exclude individuals with concomitant medical conditions that increase the risk for their participation in the study. Exclusion Criteria [53] to [57] and [60] exclude individuals who are at an increased risk for infections or infectious complications. Exclusion Criterion [58] excludes individuals who are at risk for becoming pregnant during the study. Exclusion Criterion [59] excludes individuals who are taking or who may take traditional medicines that may interfere with the ability to assess the safety and efficacy of baricitinib.

